Title: Combined therapy with rTMS and botulinum toxin in primary cervical dystonia

Principal Investigator: [name] [name]

Sub-Investigator: [name]

Primary cervical dystonia (PCD) is the most common form of focal dystonia.¹ PCD is frequently reported as a source of disability,² decreased quality of life,³ and social stigma.⁴ Botulinum toxin (BoNT) is the gold standard treatment for PCD (Class I evidence, Level A recommendations).⁴ This therapy has the advantage of avoiding central side effects such as sedation, cognitive clouding, and balance impairment, which are risks related to oral pharmacotherapy such as anticholinergic medications. Although the current standard of care is injecting no more frequently than every 12 weeks to reduce the risk of developing immunity, patients commonly report fading of benefits sooner than 12 weeks following the injection.⁵ We conducted a retrospective analysis of PCD patients injected with BoNT at our center (n=150). We found the average duration of benefits from BoNT injections was about 9.5 weeks which was also reported by other studies.⁵ Also, BoNT treatment is known to provide only pure symptomatic benefits and does not seem to modify the disease pathophysiology.^{3,4,6} Thus although BoNT therapy is the first-line approach for treatment of PCD, in many patients it provides only suboptimal benefits. Therefore there is clearly a merit in exploring other options to potentiate and possibly prolong the benefits of BoNT therapy.

We propose to use repetitive transcranial magnetic stimulation (rTMS) therapy as an adjunctive therapy in combination with BoNT injections as a novel approach to treat PCD. rTMS refers to the application of transcranial magnetic stimulation (TMS) pulses to a specific target at predefined stimulation parameters.⁷⁻⁹ The fundamental mechanism of action for rTMS is modulation of brain excitability. rTMS therapy has shown beneficial results in many neurological and psychiatric conditions.⁷⁻¹⁰ rTMS therapy is FDA approved for treatment of medication refractory depression.^{7,11} rTMS at frequencies of 5-Hz and higher has been found to transiently enhance excitability, ^{7,12} whereas rTMS at frequencies of 1-Hz and lower has been found to depress cortical excitability.^{7,13} Repeated sessions of rTMS therapy have been demonstrated to induce cumulative persistent benefits that can last weeks after the conclusion of the rTMS sessions. For example, in a recent double blind randomized controlled study, low frequency rTMS delivered over eight weeks to Parkinson's disease patients showed positive clinical benefits that lasted for 12 weeks beyond the last rTMS session.¹⁴

The **primary goal** of this study is to compare standard treatment with BoNT versus BoNT combined with a one week course of rTMS. Although the pathophysiology of dystonia has been traditionally regarded as a disorder of the basal ganglia-motor cortex network, there is increasing evidence to show that the cerebellum plays an important role. The cerebellum in dystonia has been found to be defective both at a structural and functional levels.¹⁵ Several neuroimaging studies have shown an abnormally increased activity in the cerebellum.¹⁶⁻²¹ High frequency rTMS of the cerebellum was found to modulate the sensorimotor plasticity response in dystonia.⁸⁻¹⁰ Thus there is now significant evidence to show that cerebellum in the brain plays an important role in pathophysiology of dystonia. The cerebellum has been found to be defective both at a structural and functional levels. We therefore plan to use cerebellum as our target of stimulation in our study.

The **central hypothesis** of this study is that rTMS therapy in PCD can potentiate the effects of BoNT injections. With the current standard treatment, the peak-dose benefits seen with BoNT are seen at about 4-6 weeks after the administration of injections. We plan to introduce a 1 week course of rTMS around 2-8 weeks before or after BoNT or T1). We may examine the effects of combined therapy at around 10 weeks after BoNT (T2) and at around12 weeks after BoNT (T3) injections follow-up (Figure A). We will record the clinical outcome with the Toronto Western Spasmodic Torticollis Rating Scale (TWSTRS), a standardized validated rating scale for PCD. We will also measure the physiological effects at these time points with transcranial magnetic stimulation (TMS) technique, a useful tool to understand the brain physiology. We will measure the effects of rTMS on cerebellar excitability with a well-established TMS parameter referred to as cerebellar inhibition (CBI). As mentioned in aforementioned section, rTMS delivered at 1 Hz and below inhibits the brain

4/20/2015

and when delivered at frequencies greater than 5 Hz, ^{7,11-13} it excites the brain. Based on previous imaging studies that showed increased activation of cerebellum in dystonia, ^{16-21,28} we plan to use low frequency rTMS to achieve inhibition of cerebellum and improvement of symptoms.

It is reasonable to be concerned that the alongside the effects of low frequency rTMS on excitatory loops, the inhibitory loops in the cerebellum could as well be further inhibited by rTMS. We are therefore planning to include the cerebello-cortical inhibition circuit to determine the effects of rTMS on an inhibitory loop.

[figure not shown]
SPECIFIC AIM 1: Clinical impact of rTMS therapy in PCD.

[figure not shown]
We will determine the clinical effects of 1-Hz rTMS therapy of the cerebellum when combined with BoNT injections in PCD. Comparisons will be drawn in the clinical scoring of TWSTRS (blinded videotape ratings) between T1 (around 6 weeks after BoNT injections or the start of rTMS therapy), T2 (around 10 weeks after) and T3 (around 12 weeks after or at the time of next BoNT injection) assessments. We hypothesize benefits seen at T2 follow-up compared to T1 will be greater in the group receiving combined rTMS and BoNT therapy compared with standard BoNT alone. Similar effects will be seen at T3 follow-up but they will be reduced in magnitude. (Figure C)

[figure not shown]
SPECIFIC AIM 2: Physiological impact of rTMS therapy in PCD

Aim 2a: We will determine the physiological effects of 1-Hz rTMS therapy when combined with BoNT injections in PCD. We will record the time course of effects on cerebellar inhibition (CBI) at T1, T2 and T3 follow-ups by MAGSTIM system. We hypothesize that compared to T1, CBI will be reduced and reach physiological levels at T2 follow-up. CBI will continue to remain at physiological levels at T3 follow-up though to a lesser extent.

Aim 2b: We will determine if the physiological effects of 1-Hz rTMS therapy as reflected in CBI, will correlate with the clinical scoring of PCD symptoms. We hypothesize that the change in CBI measure at T2 and T3 follow-ups will show positive correlation with the improvement in PCD symptoms at these time points.

4/20/2015

STUDY DESIGN: Subjects receiving BoNT therapy for a diagnosis of PCD will be enrolled. Diagnosis of PCD will be established in accordance with the Consensus Statement of the Movement Disorders Society.²⁷ In this two year study, we plan to recruit 20 subjects with PCD in the age range 21-80 years. Subjects followed at our center regularly fill out a self-reported form to document the duration of benefits they perceive with BoNT therapy. We will enroll subjects who report benefits lasting 10 weeks or less only (suboptimal benefits with standard care). Specifically, our inclusion criteria are: 1) Diagnosis of PCD according to the Consensus Statement of the Movement Disorders Society; 2) Report benefits of BoNT lasting 10 weeks or less only. We will exclude subjects with 1) pregnancy; 2) active seizure disorder 3) presence of a metallic body such as pacemaker, implants, metal rods and hearing aid. We will also identify subjects who meet inclusion/exclusion criteria from the IRB approved database (#416-2002). These subjects have consented to be contacted for future research. We will enroll 10 healthy age and sex-matched controls for normative electrophysiological data. Controls will be recruited through fliers placed across the campus. Specifically, our inclusion criteria are: 1) There is no history of any neurological disorders; 2) Neurological exams are unremarkable. We will exclude subjects with 1) pregnancy; 2) any neurological disorders 3) presence of a metallic body such as pacemaker, implants, metal rods and hearing aid.

Eligible subjects will be invited to an introductory session. We will obtain IRB approved informed consent. Subjects will be explained in detail about the procedures outlined for the study. Subjects will have a detailed medical history and neurological examination using the NINDS Common Data Elements. Subjects will be randomized to receive BoNT therapy combined with real or sham rTMS (1:1, 10 subjects in each arm). At our center, PCD subjects are scheduled for BoNT injections approximately every 12 weeks. rTMS therapy will be administered in the period around 2-8 weeks before or after the BoNT injections. Although the physician administering TMS will be aware of the status of the subject in terms of real TMS versus sham-TMS, this physician will play no role in any of the outcome measures, and will not be present during any of the outcome measure assessments. Similarly, the investigator who performs the outcome measures will not be present during any of the TMS sessions, and therefore will remain blinded to the status of the patients with respect to real rTMS versus sham rTMS.

Outcome measures. The clinical outcome will be measured with Toronto Western Spasmodic Torticollis Rating Scale (TWSTRS). The TWSTRS is a widely accepted composite rating scale for PCD with subscales for clinical severity, functional disability, and associated pain. Studies evaluating the clinimetric properties of TWSTRS have demonstrated substantial reliability, validity, and responsiveness to change following therapeutic intervention. It is the most commonly employed outcome measure in PCD trials and has practical applicability in a clinical setting. Also, we will administer the Craniocervical Dystonia Questionnaire Description for quality of life assessment. The Craniocervical Dystonia Questionnaire (CDQ-24) is a patient-rated health related quality of life (HR-QoL) measure for craniocervical Dystonia on 5 HR-QoL domains. It is composed of 24 items, forming 5 subscales: stigma, emotional well-being, pain, activities of daily living, and social/ family life. Items are rated on a 5-point scale.²³ Each item consists of five statements representing increasing severity of impairment, scored from 0 to 4. Subjects will be instructed to indicate how they have felt during the past two weeks because of dystonia by selecting one of the five statements for each item. Subjects will also rate their symptoms before and after stimulation using a 7-point nominal scale: 1) excellent, 2) very good, 3) good, 4) average, 5) slightly worse than usual, 6) bad or 7) very bad.

We will record videos of subjects at T1, and possibly at T2 and T3 time points which will be scored by two independent blinded raters (excluding control patients). We will obtain IRB approval to consent subjects in order to obtain videos of all subjects (excluding control subjects). The physiological outcome will be measured with TMS (CBI measure). We will also obtain MRI scan before and after rTMS therapy.

Brain Structure Measures: We will be using the research dedicated 3T Phillips or 3T Siemens MRI scanners in the McKnight Brain Institute to obtain diffusion tensor imaging, T1 weighted, and T2 weighted images. ²¹ We will be using the 32 channel head coil (Phillips) or 64 channel head coil (Siemens) for data acquisition.

Brain Function Measures: We will be using the research dedicated 3T Phillips or 3T Siemens MRI scanners at the McKnight Brain Institute to obtain functional magnetic resonance imaging (fMRI) data during the production of grip force production tasks²²⁻²⁴. Participants will use their hand to squeeze an MRI compatible

grip force transducer in the MRI unit. This is a fiber optic transducer that is fully compatible with MRI. When producing force, the participants will view the amount of force they generate when viewing the visual feedback on a MRI compatible visual display while lying inside the scanner.

RTMS THERAPY:

Real stimulation: Repetitive-TMS will be delivered over each cerebellar hemisphere, using a NeuroStar TMS therapy system (Neuronetics, Malvern, PA, USA).²² This coil, delivering TMS pulses to the patient's brain, will be positioned over a point that is 3 cm lateral to the inion on the line joining the inion and the external auditory meatus. The coil position will be marked on the skin. 900 pulses will be delivered consecutively to each side with a frequency of 1 Hz and at an intensity of 90% of the resting motor threshold (RMT) for a total duration of 15 min for each cerebellar hemisphere. The RMT will be defined as the lowest stimulation intensity required to evoke a 50 µV potential in a target muscle (i.e. first dorsal interosseus muscle in our case). Constant coil position will be continuously monitored during the experiment. During rTMS, all patients will wear ear plugs in order to protect the ears from the acoustic artefact associated with the discharge of the stimulation coil. A similar protocol will be observed for the contralateral cerebellum.

Sham Stimulation: Patients will undergo the same procedure for identifying stimulus location used in patients receiving real rTMS. Simulated rTMS will be administered using NeuroStar TMS therapy system coil which produces discharge noise and vibration without stimulating the cerebral cortex. This technique has been suggested to provide more effective blinding compared to other methods use in previous controlled studies.²³

Safety of rTMS: Repetitive TMS can have undesired side effects.²⁴ The proposed study will use TMS parameters well within the published safety guidelines adopted by the International Federation for Clinical Neurophysiology and subsequently updated.^{25,26} We will conduct careful monitoring of the participants and follow all recommended precautions for the application of TMS.

Data Safety Monitoring Plan

The principal investigator monitors the patient safety and data collection of each study visit. If she feels there is possible harm to subject safety or the possibility of, any harm due to something new that was learned during the study, she will convene a multi-disciplinary committee of at least 2 health professionals to perform a thorough review of the study details.

Regulatory Approval, Statistics, Time Line

The study will be approved by the University of Florida Institutional Review Board, and all subjects will provide informed consent. The study is highly feasible given the large number of PCD subjects seen at UF and the considerable expertise. Statistical analyses will be performed using commercially available statistical software (SPSS, version 19.0; SPSS, Inc., Chicago, Illinois). We aim to enroll 20 subjects for this pilot study, and 10 control subjects. For Aim1 and 2a, we will conduct a mixed model analysis using time and stimulation arm as repeated factors adjusted for baseline values, and subjects as the random factor. The model will include 2 factors: treatment (2 levels: real vs sham) and time (3 levels: T1, T1, and T3). The 2-tailed significance level will be set at 0.05 For Aim 2b, we will use Spearman correlation test to determine the relation between the change in CBI at T2 compared to that at T1 and change in CBI at T3 compared to that at T1. With an expected difference of 30% in TWSTRS scores at 10 weeks between the two arms (real and sham rTMS), a standard deviation of 20%, type I error of 5% and power of 80%, the necessary sample size for each group is ten completers.

TIME AND EVENTS TABLE

Description	Screenin g	rTM S V1	rTM S V2	rTMS V3	rTMS V4	rTMS V5	10 wk FU*	12wk FU*
Consent	Х							
Neurological Exam	Х							
Med History	Х							
Inclusion/Excl.	Х							
Botox Injection (SOC)	X							
Randomization	x							
MRI		Х				Х		
rTMS (real/shame)		Х	Х	Х	Х	Х		
Determine Threshold	X							
Videotape		Х				Х	х	Х
Blinded Rater Eval		Х				Х	х	Х
Urine pregnancy	x							
CDQ 24	Х					Х	Х	Х
Clinical Assessments								
TWSTRS		Х				Х	Х	X

Physiological Tests						
CBI measured with TMS	X			Х	Х	Х

*optional

References:

1. Fahn S (Ed): Movement disorders 2. London: Buttersworth; 1987.

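### The 10-week TWSTRS rating is the only powered time point, yet the schedule marks that visit optional and the text leaves it discretionary

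*Combined protocol and SAP*

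**What the plan says.** Three places in the combined protocol and SAP make the 10-week assessment (T2) discretionary:

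- The central-hypothesis paragraph: "We may examine the effects of combined therapy at around 10 weeks after BoNT (T2"). The same sentence covers T3, at about 12 weeks.
- Outcome measures: "We will record videos of subjects at T1, and possibly at T2 and T3 time points".
- The Time and Events Table: the 10-week and 12-week columns carry an asterisk, and its footnote reads *optional*. TWSTRS, videotape and blinded rating are all marked in those two columns.

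Other places treat the assessment as certain:

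- Specific Aim 1: "Comparisons will be drawn in the clinical scoring of TWSTRS (blinded videotape ratings) between T1", T2 and T3. Its lead hypothesis is "We hypothesize benefits seen at T2 follow-up compared to T1 will be greater in the group receiving combined rTMS and BoNT therapy". For T3 it adds: "Similar effects will be seen at T3 follow-up but they will be reduced in magnitude".
- Aim 2a: "We will record the time course of effects on cerebellar inhibition (CBI) at T1, T2 and T3 follow-ups". Aim 2b: "We hypothesize that the change in CBI measure at T2 and T3 follow-ups will show positive correlation with the improvement in PCD symptoms".
- Regulatory Approval, Statistics, Time Line: the sample size assumes a 30% difference in TWSTRS at 10 weeks, SD 20%, type I error 5% and power 80%, and asks for ten completers per group. The Spearman analysis for Aim 2b uses changes from T1 to T2 and from T1 to T3.
- Study Design: "Subjects will be randomized to receive BoNT therapy combined with real or sham rTMS (1:1, 10 subjects in each arm").

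No section makes T2 mandatory, says at whose option the visit is, or defines a completer.

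**The concern.** The measurement on which the trial is sized may, on the plan's own wording, never be taken. Staff who follow the schedule could omit T2 without deviating from the protocol. Randomisation equals the completers required, so enrolment contains no allowance for missed visits. A subject who skips T2 could also be counted as a completer, because the term is undefined.

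Two things are at stake. The first is information: with few T2 ratings the powered contrast is imprecise, and with none it cannot be estimated. The second is bias: attendance at an optional visit may depend on how much benefit the subject feels. If the planned mixed model is fitted by likelihood (the plan does not say), it keeps subjects who lack T2. It does not restore the missing T2 information, and it does not remove bias when missingness depends on the unseen T2 score.

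**Working it through.** **Inputs from the plan.** Difference 30, SD 20 (both in the plan's percentage units), two-sided 0.05, power 80%, 10 randomised per arm. Attendance and all correlations below are assumptions, because the documents give none.

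**1. The plan's own figure.** Normal approximation: n = 2(1.960 + 0.842)² × (20/30)² = 6.98, so 7 per arm. Exact two-sided t-test: power is 79.7% at 8 and 84.8% at 9, so 9 per arm. The stated 10 is therefore supported and slightly conservative. It presumes a T2 rating from all ten.

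**2. Power as T2 ratings are lost, t-test.** Noncentrality = 1.5/√(2/n), with 2n − 2 degrees of freedom.

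| Rated per arm | Noncentrality | Power |
|---|---|---|
| 10 | 3.354 | 88.7% |
| 9 | 3.182 | 84.8% |
| 8 | 3.000 | 79.7% |
| 7 | 2.806 | 73.1% |
| 5 | 2.372 | 54.9% |

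**3. Power with baseline adjustment.** The planned model adjusts for baseline. I approximate its T2 contrast by an ANCOVA of T2 on T1 and arm (2n − 3 degrees of freedom, simulated), taking SD 20 as the unadjusted SD.

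| Rated per arm | T1–T2 correlation 0.3 | 0.5 | 0.7 |
|---|---|---|---|
| 10 | 89.5% | 94.2% | 98.9% |
| 8 | 79.8% | 86.7% | 96.0% |
| 7 | 72.8% | 80.5% | 92.5% |
| 5 | 52.2% | 60.0% | 75.7% |

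If SD 20 is instead the SD of change, power at correlations 0.3 / 0.5 / 0.7 is 85.6 / 80.6 / 75.4% with 7 per arm and 65.8 / 60.0 / 54.8% with 5.

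**4. Expected power by attendance.** With independent Binomial(10, p) attendance in each arm and correlation 0.5, attendance of 90, 80, 70 and 50% gives 90.8, 85.6, 78.2 and 55.4%.

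**5. Can T3 stand in for T2?** Suppose 3 per arm miss T2 but everyone has T3 (T1–T2 and T1–T3 correlations 0.5, T2–T3 correlation 0.7). The standard error of the T2 contrast falls from 9.65 to 9.22, against 7.98 with nothing missing. Most of the lost information is not recovered.

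**6. Illustrative bias.** Let a fraction m of one arm miss T2, with correlation r between missingness and the T2 score. The shift in that arm's mean is r × 20 × φ(z_m)/(1 − m), where φ is the standard normal density and z_m is the standard normal quantile at m. For m = 0.3, φ(z_m)/(1 − m) = 0.497, giving 2.98 at r = 0.3 and 4.97 at r = 0.5. For m = 0.2 it is 0.350, giving 2.10 and 3.50. These are the biases when nobody is missing in the other arm. With 30% against 20% missing, the difference is 0.88 to 1.47. Baseline adjustment (correlation 0.5) lowers the one-sided cases to about 2.3 to 3.9 (m = 0.3) and 1.6 to 2.7 (m = 0.2). Baseline-adjusted type I error is 5.7 to 6.7% with 7 against 10 rated, and 5.1 to 5.7% with 7 against 8.

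**The case against.** The best counter-argument has four parts.

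- **Direction.** Three separate places leave T2 discretionary. That may be a deliberate relaxation that was never carried through to the aims, so re-basing Aim 1 on another assessment would also reconcile the text. This is a fair reading of the wording, and only the sponsor knows the intent.
- **A required rating exists.** The Time and Events Table has unstarred TWSTRS, videotape and blinded rating at the fifth rTMS visit, so a blinded post-treatment score is due even if nobody attends T2. This limits the harm. But that visit falls at the end of stimulation and is not a time point in the aims or the model. Using it would change the trial's question from lasting benefit to immediate effect.
- **Video is not the same as TWSTRS.** The table lists TWSTRS separately from the video and the blinded rating, so a missing video need not mean a missing score. True, but Aim 1 specifies blinded videotape ratings, and the star covers the whole visit.
- **Size.** This is a 20-patient pilot, the losses are assumed, and one or two per arm do little damage. That also stands. It does not remove the contradiction, because the plan still states a two-tailed test, a power target and a 10-week endpoint.

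**Conclusion.** The concern holds, and the passages must be reconciled before follow-up, since a missed 10-week rating cannot be collected afterwards. The finding rests on the text alone: the single powered comparison depends on a visit the schedule labels optional, and nothing elsewhere cures that. The sample-size arithmetic is sound.

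The numbers show how much slack there is. One or two lost ratings per arm are tolerable (79.7% or more by t-test). Three may be (72.8 to 92.5% across the assumptions tried). Five are not (at most 75.7%). Bias of up to about 5 percentage points is modest against a planned difference of 30. The larger risk is T2 going unrated in many or all subjects, and the documents give no basis for putting a probability on it.

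T3 has the same conflict but carries no power statement. Aim 1 allows it to coincide with the next injection, so it may be easier to obtain.

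**What to change.** 1. Make the T2 TWSTRS, video and blinded rating required for every randomised subject. Remove the asterisk from the 10-week column, and replace the permissive wording for T2 in the central-hypothesis paragraph and in Outcome measures with a firm commitment.
2. In the statistics section, name real versus sham at T2 as the powered comparison. Correct the model's time levels there too: the second is printed as a repeat of T1, and T2 is evidently meant (a minor point that adds nothing to the severity).
3. Report missed T2 ratings, with reasons, by arm.
4. For T3, either require it as well or state which T3 parts of Aims 1, 2a and 2b are exploratory and may be incomplete.

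If the sponsor does intend T2 to be optional, Aim 1 and the sample size must be rebuilt on an assessment that is required, with the change of question acknowledged.

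**Cost.** A few wording changes and one or two asterisks. The 10-week visit already has a column in the schedule, but routine injection visits are about 12 weeks apart, so for most of the 20 subjects it is likely to be an extra attendance that becomes firm. Requiring T3 adds a firm 12-week visit. None of this settles what the 10 weeks are counted from when rTMS precedes the injection, which is a separate matter.

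### T1, the reference visit for every aim, has two anchors that agree only if rTMS starts near week 6, and the model's baseline is tied to neither

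*Combined protocol and SAP*

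**What the plan says.** All places are in the combined protocol and SAP.

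- **Specific Aim 1** gives T1 two anchors: "T1 (around 6 weeks after BoNT injections or the start of rTMS therapy), T2 (around 10 weeks after". It then gives "T3 (around 12 weeks after or at the time of next BoNT injection) assessments".
- **Central hypothesis paragraph**: "We plan to introduce a 1 week course of rTMS around 2-8 weeks before or after BoNT or T1". For the follow-up: "We may examine the effects of combined therapy at around 10 weeks after BoNT (T2". It also states that "the peak-dose benefits seen with BoNT are seen at about 4-6 weeks" after injection.
- **Study Design**: "rTMS therapy will be administered in the period around 2-8 weeks before or after the BoNT injections", and "PCD subjects are scheduled for BoNT injections approximately every 12 weeks".
- **Outcome measures**: "We will record videos of subjects at T1, and possibly at T2 and T3 time points".
- **Time and Events Table**: BoNT is marked once, at screening. TWSTRS, video and blinded rating are first marked at rTMS V1, then at V5 and at the optional 10-week and 12-week follow-ups. No column is labelled T1, week 6 or baseline.
- **Regulatory Approval, Statistics, Time Line**: the mixed model for Aims 1 and 2a adjusts for baseline values but names no visit. Its only factors are treatment (real or sham) and time. Time has three levels, but the list prints T1 twice and omits T2.

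**The concern.** T1 is the reference for everything the trial sets out to show. Aim 1 compares the benefit at T2 with T1 between arms, Aim 2a describes CBI relative to T1, and Aim 2b uses changes in CBI from T1. Two analysts working from the Specific Aim 1 wording could pick different visits, one before stimulation and one after it. A post-treatment reference would remove part of the effect under study.

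The model adds a second gap. If the unnamed baseline is T1, the same measurement is both a covariate and one of the three outcome levels. In a model with only treatment and time as factors, the arm effect then averages in a visit at which no rTMS effect can exist.

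**Working it through.** **The plan's own figure.** The inputs in the statistics section are a difference of 30%, SD 20%, two-sided 5% and 80% power. The normal approximation gives 2 × (1.960 + 0.842)² × (20/30)² = 6.98, so 7 per group. The t-test version gives 8.06, so 9 per group. The stated ten completers per group is therefore reproduced, slightly on the safe side; power at 10 per group is 88.7% by t-test. This calculation rests on the arm difference at 10 weeks and does not use T1.

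**Do the two anchors agree?** Let s be the week of rTMS start after BoNT. The gap between the week-6 anchor and the start-of-rTMS anchor is 6 − s.

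| Start s | 6 − s (weeks) | Status of the one-week course at week 6 |
|---|---|---|
| 2 | +4 | complete |
| 5 | +1 | just complete |
| 6 | 0 | anchors agree |
| 8 | −2 | not begun |

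A course is complete by week 6 when s + 1 ≤ 6, that is, for starts in weeks 2 to 5.

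**Consequence for the T1-to-T2 contrast.** Write D1, D2 and D3 for the rTMS effect (real minus sham) at T1, T2 and T3. The between-arm contrast in change is D2 − D1. If T1 precedes stimulation, D1 = 0 and the contrast is D2. If T1 follows a completed course, D1 is subtracted. The documents give no figure for D1. The background does say that repeated sessions can have benefits lasting weeks, so D1 cannot be presumed zero.

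**Intervals if T1 = V1.** With rTMS after BoNT, T1 to T2 is 10 − 8 = 2 to 10 − 2 = 8 weeks. With rTMS before the next injection, a 12-week cycle, and T2 counted from the current injection, the start lies at week 12 − 8 = 4 to 12 − 2 = 10. T1 to T2 is then 0 to 6 weeks, and at the late limit T2 falls due as the course begins. These are nominal limits of windows that the plan itself calls approximate. The text does not say which injection T2 and T3 are counted from when rTMS comes first.

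**T1 as both covariate and outcome level.** Assume complete, balanced data, a random subject intercept and a pre-stimulation T1 (D1 = 0).

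- The subject mean over three visits is (T1 + T2 + T3)/3 = T1/3 + (2/3) × (T2 + T3)/2.
- Once T1 is a covariate, the first term is absorbed. The arm coefficient is (0 + D2 + D3)/3, against (D2 + D3)/2 when only T2 and T3 are outcomes. The ratio is 2/3.
- The standard error carries the same factor of 2/3, so the t statistic does not change.
- Check: 4,000 simulated trials, 10 per arm, assumed D2 = 1 and D3 = 0.5. The formulas give 1.5/3 = 0.500 and 1.5/2 = 0.750. The simulation gave 0.500 and 0.750, ratio 0.667.
- A treatment-by-time contrast of T2 against T1 has expectation D2 − 0 = D2 and is not shrunk.

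**The case against.** The strongest reply is that the documents largely settle T1. TWSTRS, video and blinded rating first appear at V1, the two follow-up columns match T2 and T3, and there is no week-6 visit at which a post-treatment T1 could be taken. The central hypothesis sentence also ties T1 to the rTMS course. Most of this stands: T1 = V1 is the better-supported reading, and it causes no dilution. But nothing in the text equates V1 with T1 or with the model baseline. The Specific Aim 1 wording can even be read as six weeks after either BoNT or rTMS start, which would be post-treatment. Figure A, which is not shown in the text reviewed, may give the intended timeline, but text and table would still have to match it.

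A second reply is that the two-thirds factor is only a rescaling and that Aim 1 is in substance a treatment-by-time question. That is right for the test. Fitted mixed models in simulation gave only slightly lower t values when T1 was kept as a level (for example 2.32 against 2.39), many of them with convergence or boundary warnings. The reported estimate is still understated, and the plan names neither an interaction nor the contrast that answers Aim 1.

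A reader might infer three stronger points that the documents do not support:

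- **The trial will lose power through a post-treatment T1.** This needs a share of subjects assessed after treatment and an effect size at T1. The documents give neither, and the loss is zero if T1 = V1.
- **The arms will be compared with a timing bias.** Randomisation protects the week-10 comparison between arms from systematic timing differences. Varying intervals add noise.
- **The sample size is wrong.** It does not depend on T1.

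**Conclusion.** The point holds as a defect of definition with one concrete effect on estimation. The two anchors for T1 differ by up to 4 weeks in one direction and 2 in the other when rTMS follows BoNT. Only the week-6 reading puts the reference visit after treatment; the loss it would cause cannot be sized from the documents. Under the better-supported reading, T1 = V1, that loss is nil.

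Independently of timing, a pre-stimulation T1 used as both covariate and outcome level makes the arm main effect two-thirds of the post-treatment average. This assumes complete balanced data and that the main effect is what gets reported. The harm is to the reported estimate and not to the test. The plan should be corrected on both counts, although neither undermines the design.

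**What to change.** 1. Define T1 and the model baseline as the TWSTRS and CBI assessment made before the first stimulation at V1. Label V1, the 10-week follow-up and the 12-week follow-up as T1, T2 and T3 in the events table.
2. In the Aim 1 and 2a models, use T1 as the baseline covariate and T2 and T3 as the outcome levels. Include treatment-by-time, and name the arm difference at T2 as the Aim 1 contrast.
3. Correct the list of visits to T1, T2 and T3 wherever all three are described.
4. Reconcile the central hypothesis paragraph, Specific Aim 1, Study Design and the events table on the order of rTMS and BoNT and on which injection T2 and T3 are counted from. The clinical timing is the sponsor's decision.
5. Report the BoNT-to-V1 and rTMS-to-T2 intervals by arm.

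The cost is amendment wording and table labels. TWSTRS is already marked at V1. The CBI row is broken in the extracted table, so its first mark may be at screening; if it is, that measurement would move to V1.
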